#### *9.5.3.1 Definition of Baseline for Exploratory Endpoints*

For the efficacy parameters, for Study Population A, changes from Baseline will be assessed using the Visit 2 baseline data from MIV-711-201. For Study Population B, changes from Baseline will be assessed using the Visit 8 data from Study MIV-711-201 which is expected to occur on the same calendar day as Visit 1 in Study MIV-711-202. For the biomarkers in Study Population B, the baseline will be Visit 2 in the present study (MIV-711-202).

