2.5 Exploratory Objectives Study Group B

All of the above noted secondary and exploratory parameters described in Section 2.2 and Section 2.4 for study group A, are considered as exploratory objectives in study group B and will be evaluated over 26 weeks on 200 mg MIV-711 succeeding 26 weeks on Placebo.

3. Study Design

This study is a 6-month open-label one-arm extension study evaluating safety and tolerability as well as the efficacy of 200 mg MIV-711 q.d. in two separate patient populations denoted as study Group A and Group B.

Study Group A patients will be recruited from Study MIV-711-201 who were treated with 200 mg MIV-711 q.d. and whose symptoms did not clinically significantly deteriorate as defined by an increase in the numeric rating scale (NRS) of ≤ 2 compared to Baseline. Patients eligible for Study Group A will be offered 6 months' extended treatment, primarily evaluating longer term safety and tolerability. The total treatment duration of 52 weeks also allows a more suitable treatment length for the exploratory study of any structural effects of MIV-711 on joint cartilage thickness.

[figure not shown]
A further rationale of this study is to explore the treatment effect in a group of OA patients that have confirmed symptom progression over the last 6 months (Study Group B). Study Group B will be recruited from patients receiving placebo in Study MIV-711-201 who experienced a clinical worsening as defined by an increase in NRS of ≥ 2 versus Baseline. Patients eligible for Study Group B will be offered 200 mg MIV-711 q.d. for the next 26 weeks. In addition to offering the treatment to appropriate patients, this also enables the assessment of the effects of MIV-711 based on MRI imaging, symptoms and biomarkers in patients with progressing symptoms and, as such, has the potential to provide valuable information for future patient selection in OA trials. Similar to Study MIV-711-201, the joint structural endpoint of choice over 6 months treatment constitutes MRI joint bone surface measurement. All analyses, with the exception of safety and tolerability, will be conducted as exploratory with regards to Study Group B.

The analysis of data from this study will not be based on a formal statistical analysis since the primary endpoint constitutes safety and tolerability.

PAREXEL International Statistical Analysis Plan

Medivir
Protocol: MIV-711-202

Final 1.0
16 January 2018

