4.6.3 Safety Analysis Population (SAF)

The safety analysis population will be the same as the ITT population.

5. Protocol Deviations

Deviations from the protocol including violations of inclusion/exclusion criteria will be assessed as “minor” or “major” in cooperation with the sponsor. Major deviations from the protocol will lead to the exclusion of a patient from the Per Protocol Set (PPS). Deviations will be defined prior to data base hard lock.

The following criteria will be used to exclude a patient from an analysis set:

- Incorrect diagnosis
- Any of the prohibited interventions/injuries for the target knee
- Missing more than 7 doses of MIV-711
- Discontinuation from the study

Note: this is not an exhaustive list of deviations, these are only the deviations specified per protocol. The discussion during the data review meeting post data base soft lock will review all deviations collected at each site and it will be decided to which analysis set each patient belongs.

6. General Considerations for Data Presentations

In this study IMP refers to any amount of the treatments defined in section 3.5, regardless of the time or period of administration.

Data for all patients enrolled in study MIV-711-202 who receives at least one dose of IMP will be presented in the data listings.

PAREXEL International Statistical Analysis Plan

Medivir
Protocol: MIV-711-202

Final 1.0
16 January 2018

A patient who is enrolled in study MIV-711-202 but does not receive IMP will be included in those data listings for which they have data but will be excluded from all data summaries. Data summaries will only include those patients that receive IMP.

For those listings or data summaries where baseline and change from baseline measurements will be presented, unless stated otherwise, the baseline assessment to be used for calculating change from baseline will be the last valid assessment prior to first dose of 200 mg MIV-711. Note that the change from baseline will be calculated also for visits prior to the baseline visit, not only for visits succeeding the baseline visit.

Data from both studies for patients enrolled in study MIV-711-202 will be included in the data listings, tables and figures, as appropriate.

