7.9 Dose Administration

Information collected per the dose administration CRF will be listed including patient number, visit, date and time of administration, number of capsules dispensed and number of capsules returned.

The number and percentage of patients who received IMP will be summarized for each on site visit. Descriptive statistics will be used to summarize drug accountability as the number of capsules returned for each on site study visit by treatment.

Compliance will be derived as the number of days patient were exposed to IMP. 100% compliance will be considered for dosing during the period Visit 2 to Visit 5. The number of capsules used will be derived as the number of capsules dispensed minus the number of capsules returned. Subjects with less than 100% compliance will be identified among those who have results for “Reason not all unused Capsules returned”. The compliance will not be calculated for withdrawn patients, as the date of the last IMP dose taken is not captured in the database.

8. Pharmacodynamic Analysis – Efficacy

The baseline will be the last valid assessment prior to first dose of 200 mg MIV-711, i.e. the baseline visit is defined as

- Visit 2 in study MIV-711-201 for study group A
- Visit 8 in study MIV-711-201 for study group B

The exception is for the biomarkers in study group B, where the baseline visit is defined as visit 2 in the present study (MIV-711-202).

The change from baseline for visit X will be calculated as the (visit X – baseline visit) difference in observed values. Note that the change from baseline will be calculated for all visits in study MIV-711-201 and study MIV-711-202 where the actual endpoint has

PAREXEL International Statistical Analysis Plan

Medivir
Protocol: MIV-711-202

Final 1.0
16 January 2018

been observed, i.e. not only for visits in study MIV-711-202 succeeding the baseline visit.

All efficacy analyses will be made on the ITT population if not stated otherwise.

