8.1.1 Statistical Analysis – Imorphics MRI Assessments

A linear mixed effects model will be used to assess the behaviour of the MRI response over the entire period of the two studies, i.e. from visit 2 in study MIV-711-201 to visit 5 in study MIV-711-202. The model will include fixed factors for study group (A or B), visit, group*visit interaction, baseline analgesic user (Yes/No), and random effect for site and patient.

Patients considered analgesic users at baseline will be identified via concomitant medication analgesic usage. A patient exposed to a prescribed analgesic and ongoing medication at time of the first 200 mg MIV-711 intake (visit 2 study MIV-711-201 for patients in group A and visit 2 study MIV-711-202 for group B) will be considered as a baseline analgesic user.

The dependent variable in the linear mixed model is the observed MRI score. Separate mixed model analyses will be considered for each of the MRI endpoints noted in section 8.1. The following SAS code will be used as default, but a reduced model may be used in case of convergence issues:

```
PROC MIXED data=;  
  CLASS patient visit group baseline_conmed_pain_use;
```

PAREXEL International Statistical Analysis Plan

Medivir
Protocol: MIV-711-202

Final 1.0
16 January 2018

```
MODEL MRI_score = group visit group*visit baseline_conmed_pain_use/ DDFM=KR ;  
RANDOM site;  
REPEATED visit / SUBJECT=patient TYPE=UN;  
LSMEAN group*visit / diff CL ALPHA=0.1 ;  
RUN;
```

In case of convergence issues, a reduced model will be used to achieve convergence. The first two model reductions that will be considered are the following:

1. Simplify the covariance structure by using a compound symmetry covariance structure instead of unstructured.
2. Omit the random effect of site

The mean level and the change from visit 2 in study MIV-711-201 will be estimated for each population*visit combination in the model above together with the corresponding 90% confidence interval. The estimates and confidence intervals will be tabulated and visualized over visits with the two groups in the same table/figure (see example figures and example table below). In this example table and example figures (Figure 1, Figure 2 and Table 1), 'Population A' and 'Population B' refer to Group A and Group B.

PAREXEL International Statistical Analysis Plan

Medivir
Protocol: MIV-711-202

Final 1.0
16 January 2018

Figure 1 Example figure of estimated mean levels

[figure not shown]
[figure not shown]

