8.2 MOAKS MRI Assessments

The MOAKS variables below will be listed for each patient.

MOAKS Variables

- Bone Marrow Lesions (BMLs) and cysts (15 regions)
 - Number of BML cyst
 - Size of BML
 - % that is BML
- Cartilage Assessment (14 regions)
 - Size of any Cartilage Loss: 0='Normal', 1='<10% Area', 2='10-75% Area', 3='>75% Area', 9='Not Evaluable'
 - Percentage Full Thickness Loss: 0='Normal', 1='<10% Region', 2='10-75% Region', 3='>75% Region', 9='Not Evaluable'
- Osteophytes (12 regions): 0='None', 1='Small', 2='Medium', 3='Large', 9='Not Evaluable'
- Hoffa-Synovitis: 0='None', 1='Mild', 2='Moderate', 3='Severe'
- Effusion-Synovitis: 0 = 'Physiologic Amount', 1 = 'Small', 2 = 'Medium', 3 = 'Large'

For each patient and visit, the number of subregions/locations impacted by a MOAKS MRI feature will be calculated for the following variables:

- Number of BMLs and cysts.
- Size of any Cartilage Loss.
- Osteophytes

A subregion/location is considered to be by the MRI feature if it has score =1 or higher.

Shift tables by group will be tabulated for the shift from baseline to visit 5 for the number of subregions impacted by the MRI feature for the three MOAKS variables above.

PAREXEL International Statistical Analysis Plan

Medivir
Protocol: MIV-711-202

Final 1.0
16 January 2018

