Endpoint	Group	Week	N	Estimated Mean Level		Estimated Change from Visit 2 Study MIV-711-201	
				LS Mean	95% CI	LS Mean Difference from V2 MIV-711-201	95% CI
				xxxxx	A	1 (V2: 201)	nn
		26 (V8: 201)	nn	xx.xx	(x.xx, x.xx)	xx.xx	(x.xx, x.xx)
		52 (V5: 202)	nn	xx.xx	(xx.x, xx.x)	xx.xx	(x.xx, x.xx)
	B	1 (V2: 201)	nn	xx.xx	(x.xx, x.xx)		
		26 (V8: 201)	nn	xx.xx	(x.xx, x.xx)	xx.xx	(x.xx, x.xx)
		52 (V5: 202)	nn	xx.xx	(xx.x, xx.x)	xx.xx	(x.xx, x.xx)

Baseline is defined as: Visit 2 in the MIV-711-201 study for Group A and Group B

LS Mean = least squares mean, N denotes the number of Patients for each level of treatment used to estimate the LS means.

Programming note: source data obtained from: TOTAL_BML_VOLUME

PAREXEL International SAP Amendment Shells

Medivir
Protocol: MIV-711-202

Final 1.0
16 January 2018

Medivir
Protocol Number: MIV-711-202

Page X of Y

Table 14.2.2.1
Imaging variables - MOAKS Bone Marrow Lesion (BML) and Cyst
Shift from Baseline to Visit 5 Number of Subregions Impacted by MRI Feature, ITT Population

MOAKS Test/Examination Name = Number of BMLs

Group	Number of subregions affected	Baseline						
		0	1	2	3	4	5+	
A N = x	0	nn (nn.n%)	nn (nn.n%)	nn (nn.n%)	nn (nn.n%)	nn (nn.n%)	nn (nn.n%)	nn (nn.n%)
	1	nn (nn.n%)	nn (nn.n%)	nn (nn.n%)	nn (nn.n%)	nn (nn.n%)	nn (nn.n%)	nn (nn.n%)
	2	nn (nn.n%)	nn (nn.n%)	nn (nn.n%)	nn (nn.n%)	nn (nn.n%)	nn (nn.n%)	nn (nn.n%)
	3	nn (nn.n%)	nn (nn.n%)	nn (nn.n%)	nn (nn.n%)	nn (nn.n%)	nn (nn.n%)	nn (nn.n%)
	4	nn (nn.n%)	nn (nn.n%)	nn (nn.n%)	nn (nn.n%)	nn (nn.n%)	nn (nn.n%)	nn (nn.n%)
	5+	nn (nn.n%)	nn (nn.n%)	nn (nn.n%)	nn (nn.n%)	nn (nn.n%)	nn (nn.n%)	nn (nn.n%)
B N = x	0	nn (nn.n%)	nn (nn.n%)	nn (nn.n%)	nn (nn.n%)	nn (nn.n%)	nn (nn.n%)	nn (nn.n%)
	1	nn (nn.n%)	nn (nn.n%)	nn (nn.n%)	nn (nn.n%)	nn (nn.n%)	nn (nn.n%)	nn (nn.n%)
	2	nn (nn.n%)	nn (nn.n%)	nn (nn.n%)	nn (nn.n%)	nn (nn.n%)	nn (nn.n%)	nn (nn.n%)
	3	nn (nn.n%)	nn (nn.n%)	nn (nn.n%)	nn (nn.n%)	nn (nn.n%)	nn (nn.n%)	nn (nn.n%)
	4	nn (nn.n%)	nn (nn.n%)	nn (nn.n%)	nn (nn.n%)	nn (nn.n%)	nn (nn.n%)	nn (nn.n%)
	5+	nn (nn.n%)	nn (nn.n%)	nn (nn.n%)	nn (nn.n%)	nn (nn.n%)	nn (nn.n%)	nn (nn.n%)

Baseline is defined as: Visit 2 in the MIV-711-201 study for Group A and Group B

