----------------------------	------------------------	-------	-----------------------	-----------------------------------	---	---	--	-------------------------------	---

Baseline is defined as: Visit 2 in the MIV-711-201 for Group A, Visit 8 in the MIV-711-201 for Group B

PAREXEL International SAP Amendment Shells

Medivir
Protocol: MIV-711-202

Final 1.0
16 January 2018

Medivir
Protocol Number: MIV-711-202

Page X of Y

Listing 16.2.6.3
Imaging Results Imorphics - MRI of Bone Area for the Target Knee
Observed and Change from Baseline

Study Group = Group A

					Area of bone in the medial femur region, MF
Patient MIV- 711-202	Patient MIV-711-201	Visit	Date of Assessment	Score	Change Score

Baseline is defined as: Visit 2 in the MIV-711-201 for Group A, Visit 8 in the MIV-711-201 for Group B

Programming note: source data obtained from Imorphics: Area of bone in the medial femur region, MF (MF_TAB)

PAREXEL International SAP Amendment Shells

Medivir
Protocol: MIV-711-202

Final 1.0
16 January 2018

Medivir
Protocol Number: MIV-711-202

Page X of Y

Listing 16.2.6.4
Imaging Results Imorphics - MRI of Cartilage Thickness for the Target Knee
Observed and Change from Baseline

Study Group = Group A

				Average thickness of cartilage in the central medial femur region		Average thickness of cartilage in the central medial tibia region	
Patient MIV- 711-202	Patient MIV-711-201	Visit	Date of Assessment	Score	Change Score	Score	Change Score

Baseline is defined as: Visit 2 in the MIV-711-201 for Group A, Visit 8 in the MIV-711-201 for Group B

Programming note: source data obtained from Imorphics variables:
Average thickness of cartilage in the central medial femur region (CM_FEMUR_THCTAB)
Average thickness of cartilage in the central medial tibia region (CM_TIBIA_THCTAB)

PAREXEL International SAP Amendment Shells

Medivir
Protocol: MIV-711-202

Final 1.0
16 January 2018

Medivir
Protocol Number: MIV-711-202

Page X of Y

Listing 16.2.6.5
Imaging Results Imorphics - Total BML Volume
Observed and Change from Baseline

Study Group = Group A

					Combined volume of all BML regions
Patient MIV- 711-202	Patient MIV-711-201	Visit	Date of Assessment	Score	Change Score

Baseline is defined as: Visit 2 in the MIV-711-201 for Group A, Visit 8 in the MIV-711-201 for Group B

Programming note: source data obtained from Imorphics:
Combined volume of all BML regions (TOTAL_BML_VOLUME)

PAREXEL International SAP Amendment Shells

Medivir
Protocol: MIV-711-202

Final 1.0

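### Eleven SAP table shells, including three MOAKS shift tables, print a Group B baseline that SAP section 8 contradicts; built to the footnote, the MOAKS shift would be about half placebo time

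*SAP*

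**What the plan says.** **Rule in the text.** SAP section 6 gives a general rule, to hold unless stated otherwise: baseline "will be the last valid assessment prior to first dose of 200 mg MIV-711". SAP section 8 then names the efficacy visit: "Visit 8 in study MIV-711-201 for study group B", with Visit 2 of 202 for Group B biomarkers as the only exception. Protocol 9.5.3.1 agrees: "For Study Population B, changes from Baseline will be assessed using the Visit 8 data from Study MIV-711-201".

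**MOAKS.** SAP 8.2, which sits under section 8, plans that "Shift tables by group will be tabulated for the shift from baseline to visit 5" and does not repeat which visit is baseline.

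**Purpose in Group B.** SAP 2.5 says the Group B parameters "will be evaluated over 26 weeks on 200 mg MIV-711 succeeding 26 weeks on Placebo".

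**Table shells.** The MOAKS shift shells 14.2.2.1, 14.2.2.2 and 14.2.2.4 and the descriptive shells 14.2.1.1 to 14.2.1.3, 14.2.3.1, 14.2.4.1, 14.2.5, 14.2.6.1 and 14.2.6.3 print "Baseline is defined as: Visit 2 in the MIV-711-201 study for Group A and Group B". For 14.2.6.3 the footnote stands on a continuation page headed 14.2.6.4.

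**Listing shells.** The efficacy change listings print "Baseline is defined as: Visit 2 in the MIV-711-201 for Group A, Visit 8 in the MIV-711-201 for Group B".

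**Model tables.** SAP 8.1.1 plans a different contrast for both groups: "The mean level and the change from visit 2 in study MIV-711-201 will be estimated for each population*visit combination".

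**The concern.** Group B took placebo throughout study 201 and started MIV-711 only in study 202. Visit 2 of 201 is therefore the start of placebo, and Visit 8 of 201 is the last MRI and questionnaire visit before the drug. A change from Visit 2 adds the placebo half-year to the drug half-year, although SAP 2.5 keeps them apart.

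In the MOAKS shift tables the reader sees one cross-tabulation, baseline against Visit 5, with nothing to show which scan was used. If the programmer follows the footnote, the Group B table answers a different question from the planned one. If the programmer follows SAP section 8, the table is right but its footnote describes it wrongly. Either way the output as specified is faulty.

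**Working it through.** **1. Shells carrying the footnote.**

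| Type | Tables | Count |
|---|---|---|
| MOAKS shift | 14.2.2.1, 14.2.2.2, 14.2.2.4 | 3 |
| Descriptive | 14.2.1.1, 14.2.1.2, 14.2.1.3, 14.2.3.1, 14.2.4.1, 14.2.5, 14.2.6.1, 14.2.6.3 | 8 |
| Model | 14.2.1.7, 14.2.1.8, 14.2.1.9, 14.2.3.2, 14.2.4.3, 14.2.4.4, 14.2.6.2 | 7 |

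The total is 18. The 7 model tables report change from Visit 2 of 201 as SAP 8.1.1 prespecifies, which leaves 18 − 7 = 11 in conflict with SAP section 8. Five further tables are to be built as similar to these shells and would inherit the footnote: 14.2.1.4 to 14.2.1.6, 14.2.2.3 and 14.2.4.2.

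**2. Does anything else in the outputs correct the footnote?**

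- *Descriptive shells, layout.* In 7 of the 8 (all but 14.2.5), the Change cells at Visit 2 of 201 are blank for Group A and filled for Group B, so Visit 2 is not being treated as Group B's baseline. Four of these (14.2.1.1 to 14.2.1.3 and 14.2.6.3) also blank Group B at Visit 8. Table 14.2.5 fills every cell and gives no cue.
- *Descriptive shells, listings.* All 8 differ from the matching listing, which gives Visit 8 for Group B: NRS 16.2.6.2, MRI 16.2.6.3 to 16.2.6.5, WOMAC 16.2.6.14, EQ-5D-5L 16.2.6.19, e-diary 16.2.6.22.
- *MOAKS shells.* They have no visit rows and no Change column. The MOAKS listings (16.2.6.8.1 to 16.2.6.8.7) print scores by visit and state no baseline. Only the body text of SAP section 8 corrects the footnote.

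**3. Share of the Group B MOAKS interval spent on drug.**

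Inputs: 26 weeks of placebo to Visit 8 of 201, 182 ± 7 days (SAP 4.1); gap before first dose, 10 ± 5 days (protocol section 4); 26 weeks on drug to Visit 5 of 202, 182 ± 7 days (SAP 4.2). MRI windows: Visit 2 of 201 up to 7 days early, Visit 8 of 201 ± 5 days (SAP 4.1 notes), Visit 5 of 202 ± 5 days (SAP 4.2 notes).

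Formula: share = days on MIV-711 between the two scans ÷ days between the two scans.

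*From Visit 2 of 201 (the footnote):*
- Nominal: 182 / (182 + 10 + 182) = 182/374 = 48.7%.
- Lowest: scan 7 days early, 189 days of placebo, 15-day gap, 175 − 5 = 170 days on drug: 170/(7 + 189 + 15 + 170) = 170/381 = 44.6%.
- Highest: 189/(175 + 5 + 189) = 189/369 = 51.2%.

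*From Visit 8 of 201 (SAP section 8):*
- Nominal: 182/(10 + 182) = 182/192 = 94.8%.
- Lowest: scan 5 days before Visit 8, 15-day gap, 175 days on drug, final scan 5 days after Visit 5: 175/(5 + 15 + 175 + 5) = 175/200 = 87.5%.
- Highest: scan 5 days after Visit 8 with a 5-day gap, final scan no later than Visit 5: 100%.

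**4. Same type of mismatch elsewhere in Group B.**

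- *Biomarkers.* SAP section 8 says Visit 2 of 202; Listing 16.2.6.23 says Visit 8 of 201.
- *Safety.* SAP section 9 and Tables 14.3.3 and 14.3.4.1 say Visit 2 of 202; Table 14.3.4.3 and Listings 16.2.8.6 and 16.2.8.9 say Visit 8 of 201. The mean QTcF change and the QTcF change categories would then use different reference ECGs.

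**The case against.** The strongest reply is that the SAP text is unambiguous and outranks a shell footnote. SAP section 8 names the visit and governs 8.2, the descriptive layouts and listings mostly follow it, and a Visit 8 MOAKS shift can be rebuilt from scores listed by visit. Group B efficacy is exploratory and descriptive, so no test depends on it. Most of this stands. It makes the descriptive footnotes likely slips and keeps the remedy to a shell correction. It does not clear the MOAKS shells, where nothing in the outputs corrects the footnote and the printed table would mislead even if it were programmed correctly.

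Four stronger readings are tempting, and the documents do not support them:

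- *All 18 shells are wrong.* In the seven model tables the change from Visit 2 of 201 is prespecified; only the word *Baseline* in the footnote clashes with SAP section 8.
- *The SAP leaves Group B's baseline undefined.* SAP section 6 names no visit and allows exceptions, but section 8 is explicit.
- *Table 14.2.7.3 has the wrong baseline.* Its footnote (Visit 2 of 202 for Group B) agrees with SAP section 8 and 8.3.8. Its column shows change from Visit 2 of 201 and is headed that way.
- *Protocol and SAP differences would go unreported.* SAP 4.6 mentions only the analysis populations, but protocol section 9 already commits to describing and justifying any deviation from the planned analyses.

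**Conclusion.** The inconsistency is real and should be fixed before the outputs are programmed. Eleven efficacy shells state a Group B baseline that contradicts SAP section 8 and protocol 9.5.3.1. The consequence is clearest for the three MOAKS shift shells and the copy 14.2.2.3: built to the footnote, about half of Group B's interval (49% nominal, about 45 to 51%) would be on drug, against 95% (about 88 to 100%) from Visit 8. These shares assume that the schedule is kept within its stated windows and that dosing is not interrupted. They describe the time covered, not the size or direction of any change in MOAKS scores, which the documents do not allow one to estimate.

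A reader might infer that Group B's safety results would be biased. No size is claimed there: with the pre-dose ECG at Visit 2 of 202, both candidate visits precede Group B's first MIV-711 dose and lie about 5 to 15 days apart. The safety point is consistency between tables. Group A's baseline and the primary objective are unaffected.

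**What to change.** 1. **The 11 shells and their five copies.** State Visit 8 of 201 as Group B's baseline. Build the Group B MOAKS shift from the Visit 8 scan. In the descriptive shells that still fill it (14.2.3.1, 14.2.4.1, 14.2.5, 14.2.6.1), blank Group B's Change at Visit 8.
2. **The seven model tables.** Keep the prespecified column and replace *Baseline* in the footnote with *Reference visit for change*. Leave the baseline definition in Table 14.2.7.3 as SAP section 8 has it, and note that its column shows change from Visit 2 of 201.
3. **Secondary alignments for Group B.** Use Visit 2 of 202 in Listing 16.2.6.23, as SAP section 8 states, and in Table 14.3.4.3 and Listings 16.2.8.6 and 16.2.8.9, as SAP section 9 states. For the ECG outputs name the pre-dose recording, because that visit also has three post-dose ECGs.
4. **Study report.** Under the protocol section 9 commitment, record that the protocol gives other Population B baselines than the SAP: 9.5.2.1 (efficacy, Visit 2 of 202, where no MRI or questionnaire is scheduled) and 7.1 with 7.3 (vital signs, Visit 2 of 201).

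The cost is footnote and shell edits and a short note in the report. No new data or assessments are needed.

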8.3.7.1 Derived e-diary variables

Three e-diary variables will be derived:

- NRS score
- Percentage score for analgesic usage last 12 hours
- Severity and extent of their pain medication usage

For each e-diary endpoint and visit, a patient's summary value will be calculated by using the e-diary assessments recorded at the study days associated with that study visit. The study days associated with study Visit 'x' will be identified as follows: beginning at the last date of assessment associated with Visit 'x' and including up to 14 days prior to the visit recorded within 19 calendar days prior to the date of Visit 'x'. If there are less than 10 days of recorded e-diary assessment within those 19 calendar days, the summary value will not be calculated for that visit.

NRS score

The derived summary scores for e-diary NRS scores associated with each visit will be obtained as the arithmetic mean (the average) of all e-diary NRS scores observed during the study days associated with that visit (as defined above). Separate e-diary NRS summary scores will be provided for AM and PM response. In addition, the overall 24 hour summary score will be calculated as the mean of the AM and PM summary scores for each visit. The overall 24 hour summary score will only be calculated if both mean AM and mean PM scores are available.

Percentage score for analgesic usage last 12 hours

Each patient's 'pain medication usage over the last 12 hours (Yes/No)' will be calculated as the percentages of days with a YES-response of the study days associated with that visit (as defined above). This will provide each patient with a percentage score for analgesic use for each study visit and for each of AM, PM. The denominator for AM and PM percentage calculations will be the actual number of days assessed, such that the number of days is at least 10 days and less than or equal to 14 days. The overall percentage, combining AM and PM measures, will be calculated as the mean of the AM and PM percentages:

- Overall percentage = $(xx/AM \text{ denominator} + yy/PM \text{ denominator})/2$
where 'xx' is the count of AM 'Yes' responses, 'yy' is the count of PM 'Yes' responses.

PAREXEL International Statistical Analysis Plan

Medivir
Protocol: MIV-711-202

Final 1.0
16 January 2018

Severity and extent of their pain medication usage

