Each patient's summary score for severity and extent of their pain medication usage ('More than Normal', 'Normal', 'Less than normal') will be the worst (most severe) response recorded during the study days associated with each visit (as defined above). The summary score will only be calculated if the patient responded 'YES' to 'Pain medication Usage' within the study days associated with the actual visit (as defined above). Summaries will be provided by visit, with separate summary score for AM and PM. The overall 24 hour summary score will be the worst (most severe) of the AM and the PM summary score and will be calculated if the AM and the PM summary score are available.

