	WEEK 52	Median	xx.x	xx.x	xx.x	xx.x
	Min	xx	xx	xx	xx	
	Max	xx	xx	xx	xx	

Baseline is defined as: Visit 2 in the MIV-711-201 study for Group A and Group B
Table summarizes for those patients who responded Yes to the question: "Have you taken any pain medication over the last 12 hours since you last answered your OA Daily Diary?"

Programming note:

Table will be expanded to include the analysis of the following e-diary assessments:

- AM assessment
- PM assessment
- 24 Hour Overall Assessment

PAREXEL International SAP Amendment Shells

Medivir
Protocol: MIV-711-202

Final 1.0
16 January 2018

Medivir
Protocol Number: MIV-711-202

Page X of Y

Table 14.2.6.65
E-Diary Pain Medication Usage Over Last 12 Hours
Number and Percentage of Patients with each Reported Severity Category
ITT Population

Endpoint	Visit	Category	Group A N = x	Group B N = x
AM Assessment	Visit 2 MIV-711-201 DAY 1	Number of Patients [1]	nn	nn
		Less than Normal	nn (nn.n%)	nn (nn.n%)
		Normal	nn (nn.n%)	nn (nn.n%)
	VISIT 6 MIV-711-201 WEEK 14	More than Normal	nn (nn.n%)	nn (nn.n%)
		Number of Patients [1]	nn	nn
		Less than Normal	nn (nn.n%)	nn (nn.n%)
	VISIT 8 MIV-711-201 WEEK 26	Normal	nn (nn.n%)	nn (nn.n%)
		More than Normal	nn (nn.n%)	nn (nn.n%)
		Number of Patients [1]	nn	nn
	VISIT 4 MIV-711-202 WEEK 40	Less than Normal	nn (nn.n%)	nn (nn.n%)
		Normal	nn (nn.n%)	nn (nn.n%)
		More than Normal	nn (nn.n%)	nn (nn.n%)
VISIT 5 MIV-711-202 WEEK 52	Number of Patients [1]	nn	nn	
	Less than Normal	nn (nn.n%)	nn (nn.n%)	
	Normal	nn (nn.n%)	nn (nn.n%)	
		More than Normal	nn (nn.n%)	nn (nn.n%)

[1] indicates the number of patients with a YES response for each combination of visit and group

Programming note:

Table will be expanded to include the analysis of the following e-diary assessments:

- AM assessment
- PM assessment
- 24 Hour Overall Assessment

Medivir
Protocol Number: MIV-711-202

Page X of Y

PAREXEL International SAP Amendment Shells

Medivir
Protocol: MIV-711-202

Final 1.0
16 January 2018

Table 14.2.7.1
Efficacy Biomarkers from Serum and Urine Samples - Summary of Observed and Change from Baseline Values
ITT Population

Parameter = Serum CTX-I

		Group A		Group B		
		N = x		N = x		
AM/PM	Visit	Statistic	Observed	Change	Observed	Change
			N = x	N = x	N = x	N = x
		n	nn		nn	
	Visit 2	Mean	xx.x		xx.x	xx.x
	MIV-711-201	SD	xx.xx		xx.xx	xx.xx
	DAY 1	Median	xx.x		xx.x	xx.x
		Min	xx		xx	xx
		Max	xx		xx	xx
		n	nn	nn	nn	nn
	VISIT 4	Mean	xx.x	xx.x	xx.x	xx.x

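### The footnote on the e-diary analgesic-use percentage table restricts it to patients who answered Yes, contradicting SAP 8.3.7.1, under which 0% is a valid score

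*SAP*

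**What the plan says.** SAP 8.3.7.1 derives three e-diary variables. Two of them concern analgesics, and they have different entry conditions.

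- **Percentage score.** The score "calculated as the percentages of days with a YES-response of the study days associated with that visit". The text continues: "This will provide each patient with a percentage score for analgesic use for each study visit and for each of AM, PM". The denominator is the number of days assessed, "such that the number of days is at least 10 days and less than or equal to 14 days". Diary completeness is the only condition; no Yes answer is required.
- **Severity and extent of use** (more than normal, normal, less than normal). Here there is a Yes condition: "The summary score will only be calculated if the patient responded" Yes to pain medication use within the days belonging to that visit.

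SAP 8.3.7 says the derived scores are to be listed and summarised, and SAP section 8 places efficacy analyses on the ITT population unless stated otherwise.

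In SAP section 14, the shell for the percentage score (Table 14.2.6.3, whose second page is headed 14.2.6.4) is titled ITT Population and shows observed values and change from baseline. Its footnote reads "Table summarizes for those patients who responded Yes to the question" and then gives the pain-medication question. The severity shell that follows has its own footnote, under which the patient count "indicates the number of patients with a YES response for each combination of visit and group".

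Listing 16.2.6.22 keeps the two variables apart. Its note on the percentage uses days assessed as the denominator with no Yes condition. Its note on severity limits that column to Yes responses.

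**The concern.** The percentage score measures how much analgesic a patient used. A rule that admits only patients who used some selects on the quantity being summarised. The Yes condition suits the severity variable, which has no meaning without use. It does not suit a percentage for which zero is a real and favourable result.

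E-diary analgesic use is a named exploratory objective (Protocol 3.4, SAP 2.4). It also helps in reading the pain scores: analgesic changes are allowed during the study (Protocol 5.1 criterion 4, and 6.6.1), while the mixed model for the pain scores adjusts only for analgesic use at baseline (SAP 8.1.1, applied through 8.3.1.1 and 8.3.7.2). A table that drops non-users would misstate the level of use and could misstate how it changed.

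**Working it through.** The plan states no figure on this point, so there is none to reproduce. The check has three steps.

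**1. Is 0% a valid score?** SAP 8.3.7.1 sets the overall percentage to (AM Yes days / AM days assessed + PM Yes days / PM days assessed) / 2. For a patient with no Yes days:

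- 14 days assessed: (0/14 + 0/14)/2 = 0%
- 10 days assessed: (0/10 + 0/10)/2 = 0%

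Both are non-missing scores under the definition. The footnote removes them.

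**2. Effect on mean use.** If a share z of patients is removed at 0%, the printed mean is the full mean divided by (1-z). The documents give no z, so these values are assumed:

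- z = 0.10: 1/0.90 = 1.11, or 11% too high
- z = 0.25: 1/0.75 = 1.33, or 33% too high
- z = 0.40: 1/0.60 = 1.67, or 67% too high

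If Yes is judged per visit, z is the share at 0% at that visit. If Yes is judged at any time, z is the share who never answered Yes.

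**3. Effect on change from baseline.** The footnote does not say which reading applies, so both are shown. All values are assumed: 40 patients with valid diaries at baseline and Visit 5; 8 never use analgesics; 32 use them on 60% of days at baseline; s of these stop; the other 32-s continue at 50% of days.

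- All patients (8.3.7.1): change = [-10(32-s) - 60s]/40
- Yes at the visit: only the 32-s continuing users have a change, and each is -10
- Yes at any time: change = [-10(32-s) - 60s]/32

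| Stoppers s | All patients (n=40) | Yes per visit (n) | Yes at any time (n=32) |
|---|---|---|---|
| 0 | -8.0 | -10.0 (32) | -10.0 |
| 4 | -13.0 | -10.0 (28) | -16.25 |
| 8 | -18.0 | -10.0 (24) | -22.5 |
| 12 | -23.0 | -10.0 (20) | -28.75 |

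Baseline mean use is 32 × 60/40 = 48% for all patients and 60% under either reading of the footnote.

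Under the per-visit reading, the change does not respond to the number who stop; only n falls. Under the any-time reading, stoppers and starters stay in, but every change is the full value divided by 0.80, because the 8 never-users (20%) are removed. For example, -13.0/0.80 = -16.25.

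**The case against.** The strongest reply is that the SAP body already makes the right choice. Section 8.3.7.1 gives every patient with enough diary days a score, and both the table index and the shell are titled ITT. The footnote may be a leftover from the neighbouring severity table, or a loose way of identifying the question behind the title. The same shell pages carry numbering slips: the continuation page is headed 14.2.6.4, and the severity table appears as 14.2.6.65. This stands as a description: the fault is a conflict between shell and text, not a considered analysis choice. It does not remove the fault, because a programmer following the shell would exclude patients. Where the footnote came from cannot be established.

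A reader might infer more than the documents support, in three ways.

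- **That a patient who stops analgesics necessarily disappears.** This holds only if Yes is judged per visit. That reading is the likelier one, since the severity variable and its shell use Yes by visit, but the footnote does not state it. Judged at any time, a stopper keeps a 0% score at Visit 5 and the mean reduction is exaggerated.
- **That large changes in use are hidden from the report.** They are not. Listing 16.2.6.22 shows each patient's percentage and change, and the severity table prints the number of patients with a Yes by visit and group.
- **That Figures 14.2.5.3 and 14.2.5.4 share the restriction.** The figure list labels them ITT with no Yes condition, and nothing in the documents shows that they do.

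The magnitude is also wholly illustrative. The table would print its n and its footnote, so an attentive reader could recognise a mean among users only.

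**Conclusion.** The footnote contradicts the definition of the score that the table reports and should be corrected. Two consequences follow from the wording alone: never-users are dropped, and mean use is overstated wherever there are any. The effect on change depends on the reading. Per visit, stoppers and starters lose their change value, and the printed change can be too large or too small: in the example it is -10.0 against -8.0 with no stoppers, and against -23.0 with twelve. At any time, the change is inflated by 1/(1 - share of never-users).

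The size rests on the share of 0% scores, which the documents do not give; the figures above are assumptions. The reach is narrow: one descriptive table for an exploratory objective in a study that Protocol 9.2.1 says is not powered for confirmatory analysis. The primary safety objective is not affected.

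**What to change.** Replace the footnote on the percentage table with wording such as: *includes all ITT patients with a derived percentage score at the visit (at least 10 assessed diary days); 0% is counted as a value*. Keep the Yes restriction only in the severity-category table. If the number of users is of interest, add a row giving the number of patients with any Yes at the visit.

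Figures 14.2.5.3 and 14.2.5.4 need no change beyond using the same ITT patients as the corrected table.

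The cost is one footnote in a table shell. It needs no new data and no change to the derivation in 8.3.7.1.
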